3 OBJECTIVES AND ENDPOINTS

The primary outcome measurement for effectiveness is:

-The difference between the active and sham treatment groups in mean daily morphine equivalence dosage during study

Secondary endpoints include descriptive comparisons between the active and sham treatment groups in:

- The difference in mean daily headache intensity during the study

The difference between total overall morphine equivalence dosages per subject during study
 Opiate related adverse events (such as urinary retention, constipation, sedation, nausea, vomiting and pruritis)

- The difference in cytokines levels and brain permeability markers in the blood and/or CSF before and after stimulation and between the sham and active device group

- Effects of VNS on brain permeability measured through CT perfusion studies

-The difference in modified rankin scale at hospital discharge and during outpatient follow up. This will be collected retrospectively from the follow up outpatient visit.

Exploratory analyses will include descriptive comparisons of the rates of stroke, vasospasm, DCI, seizure, central fever and severity of vasospasm between the active and sham treatment groups.

OBJECTIVES	ENDPOINTS
Primary Objective:	

Incidence of device related serious adverse events.	Proportion of patients with device related adverse events
The difference between the active and sham treatment groups in mean daily morphine equivalence dosage during study	Morphine equivalence dosage will be calculated per day.
Secondary Objectives	
The difference between the active and sham treatment groups in the mean daily headache intensity during the study	Headache intensity will be measured throughout the day and a mean daily headache intensity will be calculated.
The difference between total overall morphine equivalence dosage between the active and sham group per subject during study	Total morphine equivalence dosage for the duration of the study will be calculated.
Incidence of opiate related adverse events (such as urinary retention, constipation, sedation, respiratory depression, nausea, vomiting and pruritis)	Number of patients with of urinary retention, constipation, sedation, nausea, respiratory depression, vomiting and pruritis.

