The difference in cytokines levels and blood brain permeability markers in the blood and/or CSF before and after stimulation and between the sham and active group	When possible, cytokines levels and permeability markers will be measure in the blood and/or serum just before the first vagus nerve stimulation and approximately 24 hours later, after the 11:30 AM stimulation session. If possible, this will be repeated on day 5 and 7 post-ictus as it is the period of cerebral vasospasm

	Immunologic investigations include but not limited to, measurement of inflammatory protein levels, RNA		
	sequencing of leukocyte and stimulation assays.		
Evaluate the effects of VNS on	The integrity of the blood brain barrier will be evaluated		
blood brain barrier integrity	through CT perfusion if performed as standard of care.		
Exploratory objectives			
Comparisons of the rates of stroke, vasospasm, DCI, seizure, and central fever between the active and sham treatment groups	Neuroimaging upon admission and at discharge will be compared and evidence of new strokes will be noted. The presence of DCI (change in neurologic examination thought to be due to vasospasm) will be evaluated.		
	Transcranial doppler velocities will be compared between the active and sham groups		
	The number of days with central fever will be compared between the active and sham groups		
	Incidence of seizures will be compared between the active and sham groups		
Effect of nVNS on severity of cerebral vasospasm during DSA	Rate of change in the severity of cerebral vasospasm will be noted before and during or after nVNS		

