4 STUDY DESIGN

4.1 OVERALL DESIGN

This is a single site, randomized sham controlled, double blinded, and parallel group study comparing the efficacy and safety of transcutaneous VNS in the management of headache

related to subarachnoid hemorrhage. We will screen patients diagnosed with subarachnoid hemorrhage who are admitted to Northshore University Hospital Neurosurgical Critical Care Unit. These are patients admitted under our care. Eligible patients will be enrolled after signing the informed consent. Enrollment will be performed between days 1 and 5 of aneurysm treatment. Subjects will be randomized into one of the two groups below:

- 1. Group 1: Control (patients will receive treatment using an inactive VNS device)
- 2. Group 2: Treatment (patients will receive treatment using an active VNS device)

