5.4 PRE-SCREEN FAILURES

Individuals who do not meet the criteria for participation in this trial (pre-screen failure) because of unsecured aneurysm intubated or has symptomatic hydrocephalus or symptomatic bradycardia may be rescreened once the aneurysm is secured, patient is extubated and stabilized, and EVD is placed. Rescreened participants should be assigned the same participant number as for the initial screening.

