5.5 STRATEGIES FOR RECRUITMENT AND RETENTION

The neurosurgical critical care unit (NSCU) at Northshore University Hospital is the main referral unit for the healthcare system for patients with subarachnoid hemorrhage. All transferred patients

are admitted to the NSCU, as a result, patients can be easily identified by the research team on a daily basis. Every day, the neurointensivist or the research coordinator will evaluate which patients admitted to the NSCU have been diagnosed with subarachnoid hemorrhage. If an aneurysm is found to be the cause of the SAH, surgical or endovascular treatment of the aneurysm is typically performed within 72 hours of diagnosis. Patients will be included in the study once the aneurysm has been treated. The primary investigator, or sub investigators will take consent from the patient. The primary investigator will ensure that the sub investigators and research assistants are trained and knowledgeable of the research protocol. Patients enrolled in the study will be followed up to 10 days starting 24 hours post successful treatment of the aneurysm unless discharged earlier from the hospital.

We admit on average 110 SAH cases a year. If we assume that 50% satisfy our inclusion criteria, and that 70% will sign the inform consent, we should be able to reach our target number in approximately 12 months. Patients identified in the NSCU will be approached by the research team, and the study will be explained to them.

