8 STUDY ASSESSMENTS AND PROCEDURES

8.1 EFFICACY ASSESSMENTS

Per standard of care, patients presenting with signs of SAH like acute severe headache, will get a diagnostic head CT which confirms blood in the subarachnoid space. If patients have symptomatic hydrocephalus (altered mental status with CT head consistent with hydrocephalus) an external ventricular drain will be placed. Most patients will get either a CT angiogram or a conventional angiogram to rule out a vascular malformation, especially if there is no history of trauma. If an aneurysm is detected, the standard of care is to treat it as soon as possible. Usually, an aneurysm iseither coiled or clipped (craniectomy or craniotomy). Every patient admitted with subarachnoid hemorrhage will get graded accordingly to their headache intensity, level of consciousness and neurologic deficits with the Hunt Hess grade (table 2). Their CT scans also get graded (modified fisher scale mFS) according to the thickness and location of blood (table 3). All subarachnoid hemorrhage (unless there is minimal amount of blood and no vascular malformation) are admitted to the Neurosurgical care unit (NSCU). Detailed physical examination, including the NIHSS, history, including medication history, past medical, surgical history, and social history are recorded in the medical records. North Shore University hospital NSCU is the referral center for most of the hospitals in Northwell health care system. Most aneurysmal SAH patients get transferred to our unit. Per standard of care, all women of child bearing age, admitted to the NSCU get a urine or blood pregnancy test, patients suspected of abusing drugs get urine toxicology. Once in the NSCU, patients get vital signs and neurologic assessment every hour, and pain assessment every 4 hours and as needed. The length of stay in the intensive care unit depends on the amount of blood on the head scan (mFS). Patients with higher mFS are more prone to get delayed cerebral ischemia. As a result, per standard of care, patients with SAH get almost daily transcranial dopplers to monitor for cerebral vasospasm, frequent head scans, occasionally brain perfusion studies and MRI of the brain. Patients are monitored for central fever (vital signs, blood cultures), cerebral salt wasting with frequent BMP and urine output measurements, seizures with PRN electroencephalograms (EEG). Once out of the critical care period, (vasospasm usually starts at day 3 post bleeding and peaks at day 10), patients get transferred to a regular neurosurgical floor before being discharged home or to rehabilitation. On average patients stay in the NSCU between 2-21 days. All patients admitted to the NSCU with SAH will be screened and evaluated for the inclusion and exclusion criteria after obtaining an informed consent.

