
Screening involves reviewing the medical records following HIPPA regulation for: Age, gender, ethnicity, presence of aneurysm, day of rupture, etiology of the SAH if not aneurysmal, radiologic (Angiogram, CT head) and medical history before and after the aneurysm is secured, Glasgow coma score before and after aneurysm repair, modified fisher scale (mFS), Hunt-Hess grade (HHS), time of ictus, history of alcohol and drug abuse, presence of hydrocephalus on head CT, presence of an external ventricular drain (EVD), date of EVD placement, new HHS after EVD placement, clipping or coiling. Medical records will be reviewed for the past medical history (pacemaker, defibrillator, history of CHF, arrhythmias, cervical carotid disease, history of a headache disorder like migraine or cluster headache), physical examination, labs will be reviewed which includes but not limited to pregnancy test and urine toxicology. Headache intensity and opiate, steroids and acetaminophen usage are recorded in the electronic medical record. The presence of vasospasm and delayed cerebral ischemia will be noted. Once found eligible satisfying the inclusion and exclusion criteria, and informed consent signed, patients will be randomized to either the treatment group or the control group. The same data will be recorded for both groups. The treatment period will start once admitted in the NSCU and will last for up to 10 days.

During the NSCU stay, patients areevaluated for pain every 4 hours. If vital signs are stable (SBP> 100 mmHg and HR> 60 beats per minutes with no arrhythmia on telemetry, MAP> 60 mmHg and oxygen saturation > 90%) patient will receive either the treatment (nVNS) or the Sham device every 5 hours. Headache intensity will be evaluated every four hours. In addition, vital signs will be noted just after stimulation, and hourly afterwards or as ordered by the physician. The daily mean morphine equivalence dosage will be recorded. Concomitant medications will be recorded.

During the ICU length of stay, the following will be assessed and recorded per standard of care :

- Transcranial dopplers (TCD)
- Neuroimaging (CT head, MRI brain, angiograms, CT perfusion with permeability study)
- EVD weaning and day of start of weaning
- Presence of vasospasm, delayed cerebral ischemia, Central fever, Cerebral salt wasting. These are usually recorded in the medical record.
- Urinary retention documented as frequent straight catheterization for more than 3 days

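### The exploratory new-stroke outcome uses the admission scan as its reference, so infarcts arising between that scan and the first stimulation count as new

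*Protocol*

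**What the plan says.** The exploratory objectives table in Protocol section 3 gives the only working definition of the stroke outcome: "Neuroimaging upon admission and at discharge will be compared and evidence of new strokes will be noted". The same section makes the comparison descriptive: "Exploratory analyses will include descriptive comparisons of the rates of stroke, vasospasm, DCI, seizure, central fever and severity of vasospasm".

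The timing comes from three other places. Section 5.5 says that "surgical or endovascular treatment of the aneurysm is typically performed within 72 hours of diagnosis" and that "Patients will be included in the study once the aneurysm has been treated". Section 4.1 says "Enrollment will be performed between days 1 and 5 of aneurysm treatment". Section 5.4 allows later entry for patients who at first fail screening; they "may be rescreened once the aneurysm is secured, patient is extubated and stabilized, and EVD is placed".

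Screening under section 8.1 includes review of "radiologic (Angiogram, CT head) and medical history before and after the aneurysm is secured", and the schedule of activities (section 1.2) marks imaging at screening and at enrolment/baseline. Neither place makes any of these scans the reference for new stroke.

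The SAP lists stroke among the exploratory variables without defining it. Its general baseline is visit 1 (Day 1) and is not tied to imaging. It assigns Fisher's exact test to categorical exploratory variables, two-sided at 0.05.

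**The concern.** A randomised comparison of new strokes should count events that the allocated device could have influenced. Here the clock starts at admission. The interval before first stimulation contains the aneurysm procedure, and it may contain the start of the vasospasm period, since section 8.1 notes that "vasospasm usually starts at day 3 post bleeding and peaks at day 10". Infarcts from that interval enter both arms, carry no information about the device, and pull the comparison towards no difference.

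The choice also stands apart from its neighbours. In the same table, cytokines are referenced to a sample taken just before the first stimulation, and vasospasm on angiography to its state before stimulation. No reason is given for treating stroke differently.

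At stake is how far an exploratory result can be interpreted. A later trial might draw on it for a stroke rate or an effect size, and the rate would be inflated and the effect diluted.

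**Working it through.** The documents state no stroke rate, effect size or power, so there is no figure of the plan's to reproduce.

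**Step 1: length of the gap.** Aneurysm treatment is typically within 72 hours of diagnosis, which is 3 days (section 5.5). Enrolment is on days 1 to 5 of treatment (section 4.1). If diagnosis is taken as close to admission, the gap runs from about 1 day to about 3 + 5 = 8 days. Rescreening (section 5.4) pushes entry towards the later end. The calculation applies to aneurysmal patients; those without an aneurysm have no treatment date to count from.

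**Step 2: does another rule remove these infarcts?** Section 8.3.3 treats conditions present at screening as baseline, but only for adverse event reporting. The SAP's Day 1 baseline is not linked to imaging. Nothing else in either document bears on it.

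**Step 3: effect on the comparison.** Let q be the share of patients with a new infarct between the admission scan and first stimulation, equal in expectation in both arms. Let p be an arm's stroke rate after first stimulation, taken as independent of the earlier infarct. Then:

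- observed rate = q + (1 − q)p
- observed difference = (1 − q)(p_sham − p_active)

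The ratio moves towards 1. Assumed for illustration: p_sham = 25%, p_active = 10%, and q from 0 to 30%. With 40 patients allocated 1:1 there are 20 per arm, so the expected gap in patients is 20 times the difference.

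| q | Sham | Active | Difference (points) | Ratio | Expected gap (patients) |
|---|---|---|---|---|---|
| 0 | 25% | 10% | 15 | 0.40 | 3.0 |
| 5% | 28.75% | 14.5% | 14.25 | 0.50 | 2.85 |
| 10% | 32.5% | 19% | 13.5 | 0.58 | 2.7 |
| 20% | 40% | 28% | 12 | 0.70 | 2.4 |
| 30% | 47.5% | 37% | 10.5 | 0.78 | 2.1 |

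Example at q = 20%: sham 0.2 + 0.8 × 0.25 = 0.40; active 0.2 + 0.8 × 0.10 = 0.28; difference 0.12 = 0.8 × 0.15.

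**Step 4: chance imbalance.** With 20 per arm, the difference between arms in the number of patients with a pre-stimulation infarct has standard deviation √(2 × 20 × q(1 − q)). This is 1.38 at q = 5% and 2.90 at q = 30%. From the two binomial distributions, the probability that the arms differ by two or more such patients is 25% at q = 5% and 60% at q = 30%. One patient is 1/20 = 5 points.

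**Step 5: power.** Enumerating all outcomes at 20 per arm, two-sided Fisher power at 0.05 for 25% against 10% is about 14% at q = 0, 10% at q = 10% and 5% at q = 30%.

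**The case against.** The strongest reply is that this changes little. The outcome is exploratory and descriptive in a pilot without hypotheses, and no sample size, stopping rule or primary or secondary conclusion rests on it. In the illustration the loss is 0.75 to 4.5 points, less than one patient in an arm of 20, and power is poor even with a perfect reference scan. Ratios make the effect look larger than differences do. Scans during the ICU stay are recorded as well, so many infarcts could be dated at analysis. All of this stands and sets the weight of the point. It does not defend the definition, which as written still counts events that the device could not have affected.

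The documents do not support four stronger readings that a reader might infer:

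- **All strokes before randomisation are counted.** An infarct visible on the admission scan is part of the reference and is not counted. Procedural infarcts concern aneurysmal patients only.
- **The safety assessment is compromised.** Imaging stroke is not among the safety outcomes listed in sections 8.2 and 9.4.4 or in the SAP. Section 8.3.4 treats stroke as a known complication of the disease, and section 8.3.3 gives adverse events their own baseline rule.
- **The case for neuroprotection depends on this outcome.** Section 2.3 argues it from mechanism and animal work, in conditional terms.
- **The rule favours one arm.** The excess is equal in expectation, so it creates no expected difference where none exists. In a single trial, chance can move the result either way.

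Also, the upper values of q have no source in the documents. Patients must be alert and able to report pain at enrolment, which may keep q low, though not at zero.

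**Conclusion.** The point holds in limited form. As defined, the new-stroke outcome includes infarcts arising between the admission scan and first stimulation, an interval of up to about 8 days in aneurysmal patients if diagnosis is close to admission. The direction is certain in expectation: a true risk difference is multiplied by (1 − q). The size is unknown, because neither q nor the stroke rates are in the documents. Over an assumed q of 5% to 30%, a 15-point difference becomes 14.25 to 10.5 points, with added chance imbalance at 20 per arm. The consequence is confined to an exploratory outcome. The change is worth making because it removes irrelevant events at almost no cost; it will not make a comparison of 20 with 20 conclusive.

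**What to change.** In Protocol section 3 and in the SAP's exploratory variables, define the reference for new stroke as the last available CT or MRI before the first stimulation, taken after securing in aneurysmal patients. Count as new only infarcts absent on that scan, and record its date on the CRF.

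A fallback is needed. Section 8.1 describes a review of existing records, and neither document requires a CT or MRI after securing and before first stimulation in every patient. Where no post-securing scan exists, use the admission scan, flag the patient, and report the comparison with and without flagged patients.

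The cost is a sentence or two in each document and one date field. No added imaging is required. The small downside is that some patients may lack a suitable reference scan, which the flag makes visible.

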4 STUDY DESIGN

4.1 OVERALL DESIGN

This is a single site, randomized sham controlled, double blinded, and parallel group study comparing the efficacy and safety of transcutaneous VNS in the management of headache

related to subarachnoid hemorrhage. We will screen patients diagnosed with subarachnoid hemorrhage who are admitted to Northshore University Hospital Neurosurgical Critical Care Unit. These are patients admitted under our care. Eligible patients will be enrolled after signing the informed consent. Enrollment will be performed between days 1 and 5 of aneurysm treatment. Subjects will be randomized into one of the two groups below:

- 1. Group 1: Control (patients will receive treatment using an inactive VNS device)
- 2. Group 2: Treatment (patients will receive treatment using an active VNS device)

The Biostatistics Unit at the Feinstein Institute for Medical Research [BU-FIMR] will develop a randomization plan for the study using the Biostatistics Randomization Management System [BRMS]. BRMS is a secure, HIPAA-compliant, web-based application that allows investigators to randomize subjects into randomized clinical trials (RCTs) using a personal computer with internet access. A randomization allocation will be generated by the BU-FIMR using the method of permuted blocks. Details of the randomization procedure, including required record keeping will be further developed upon approval of the protocol. The treatment group will receive 2, 2 minute stimulations every 5 hours delivered by a blinded provider. The person assessing the pain intensity, vital signs, and giving pain killers and the participants will be blinded. Pain will be rated pre and post stimulation by the blinded caregiver. During NSCU stay at each stimulation, patients will be on continuous telemetry, and vital signs will be recorded before and at the end of the treatment and hourly for the rest of the day by the blinded caregiver. The control group will receive a sham device, the device is physically identical to the active device, and however no stimulation will be delivered. Patients in either group will be informed that they might feel a tingling sensation or muscle twitch with either device. Before the stimulation is initiated, vital signs will be checked. This includes HR, SBP, MAP, and oxygen saturation. If vital signs are stable, defined as HR>60 beats per minute, SBP> 100 mmHg, MAP> 60 mm HG, and saturation > 90% on room air, nasal cannula or face mask, the stimulation will be provided. In addition, both groups will receive standard of care abortive medications. Pain is usually assessed every 4 hours and as needed, and abortive medications are given depending on the intensity of the headache. 40 patients will be enrolled, and VNS will be performed for up to 10 days.

4.2 SCIENTIFIC RATIONALE FOR STUDY DESIGN

This is a randomized sham-controlled pilot study. The patients and the person assessing the patient's response will be blinded. Standard medical care treatment will be provided to both arms of the study.

4.3 JUSTIFICATION FOR DOSE

This will be a transcutaneous stimulation of the cervical branch of the Vagus nerve to avoid the operative complications of invasive VNS. Stimulation frequency will be similar to what was has been used in studies on headache.(17) Patients will receive a dosage based on the instructions from the gammaCore IFU: the physician or patient will start stimulating the cervical branch of the Vagus nerve and will gradually increase the amplitude to the most comfortable stimulation level.

